1 INTRODUCTION

1.1 Background & Study Rationale

Adequate nutrition and appropriate nutritional interventions, like dietary supplements, can play an important role in maintaining a person's immune defenses. While frank nutrient deficiencies are not common in the United States, sub-optimal intake of several micronutrients important for the immune response has been documented in the literature. The consumption of nutrient dense foods like fruits and vegetables help individuals meet the daily recommended intakes, as established by the Institute of Medicine (IOM). The Dietary Guidelines for Americans (2020-2025) states the average intake of total vegetables, total fruits and total dairy is less than recommended intake ranges for ages 14 and up (1). Additional supplementation of essential nutrients at levels well-below upper safety levels as established by the IOM, provides an effective way to supplement the diet, optimize micronutrient status, and support immune function.

The human immune system is the body's natural way to protect itself. It is constantly working to protect the body from infection, injury, and disease. Vitamins and minerals are essential for the integrity and optimum function of the immune system (2,3). An adequate supply of nutrients is required for the immune system's baseline functions as well as for ramping up its activity when necessary. It is well established that micronutrient status plays an important role in the immune response and that deficiencies in one or more essential micronutrients can diminish immune function (2,3).

Vitamin C is an essential nutrient that plays an important role in the immune system. In addition to vitamin C, Emergen-C products contain a variety of additional immune supporting nutrients to provide a more comprehensive immune support formula compared to products just containing vitamin C.

Emergen-C core powders contain a variety of nutrients (vitamin C, zinc, vitamin B6, vitamin B12, folate, manganese) that are critical for maintaining proper immune function. Vitamin C, zinc, and manganese are powerful antioxidants. The oxidant-antioxidant balance is an important determinant of immune cell function, including maintaining the integrity and functionality of membrane lipids, cellular proteins, and nucleic acids and controlling signal transduction and gene expression in immune cells. Optimal amounts of antioxidants are needed to maintain and support the immune response across all age groups.

Vitamin B12, folate and vitamin B6 have an essential role in the production and development of all new cells in the body, including immune cells. This process is crucial for the immune system to maintain its normal functions and to ramp up production when needed to respond to foreign invaders.

Much of the research investigating high vitamin C supplementation has focused on its impact on the common cold (4-9). In 1971, Linus Pauling carried out a meta-analysis of vitamin C and the common cold, including the four placebo-controlled trials available at that time. He

Property of Haleon- Confidential

May not be used, divulged, published or otherwise disclosed without the consent of Haleon

CCI [REDACTED] Abbreviated Clinical Protocol Template v1.0

found very strong evidence that vitamin C decreased morbidity caused by the common cold ($P = 0.000022$) (10,11). Subsequent larger and methodologically more robust randomized controlled trials (RCTs) supported Pauling's conclusions. In a recent Cochrane review on vitamin C and the common cold, regular vitamin C supplementation of ≥ 0.2 g/day shortened the duration of colds by 9.4% ($P < 0.00001$) (10,11). Nevertheless, despite the strong evidence indicating that vitamin C has physiological effects on the common cold, there is a persistent wide-spread belief that vitamin C is of no benefit.

While the available evidence shows that vitamin C can affect colds, the optimal doses and the size of maximal benefit are not known, although two controlled trials indicated that 6–8 g/day of vitamin C might be twice as effective as 3–4 g/day (12-17).

Despite the research there are no current clinical recommendations that support the possibility of the potential impact on the risk of infection and of significantly reducing the severity of respiratory infections, by using high-dose supplements of vitamin C in a well-nourished general population. Only in restricted subgroups (e.g., athletes or the military) and in subjects with a low plasma vitamin C concentration may a supplementation be justified. Furthermore, in categories at high risk of infection (i.e., the obese, diabetics, the elderly, etc.), vitamin C supplementation can modulate inflammation, with potential positive effects on immune response to infections. The impact of an extra oral intake of vitamin C on the duration of a cold and the prevention or treatment of pneumonia is still questioned.

Other research into high doses of vitamin C has investigated how supplements have impacted physical and emotional measures of health. The B-vitamins are widely accepted as playing a role in brain function, and there is evidence to suggest that B-vitamins may have a modifying effect on cognitive function. Therefore, much of the research into B12 and B6 has investigated the impact of these vitamins on cognition as well as mood and stress.

Vitamins and minerals and their impact on quality of life in terms of energy and cognition is an area of increasing interest (18). A recent meta-analysis of vitamin C supplementation on mood status in adults showed that it may be beneficial in certain populations (19). A meta-analysis of the effects of vitamin and mineral supplementation on stress, mild psychiatric symptoms, and mood in nonclinical samples showed that subjects taking supplements with high levels of vitamin C and B-vitamins had lower levels of stress, improved mood, and better energy than placebo (20).

An extensive literature review investigating the research behind immune supplements (with high levels of vitamin C and the B-vitamins) showed that high doses of vitamin C can lead to increased levels of perceived energy. Twenty-nine studies have looked at the impact of supplement brands on various aspects of physical health, psychological health, and emotional including supplements such as Berocca, Supradyn, Elevit, and Centrum. Berocca and Supradyn (manufactured by Bayer) contain high levels of vitamin C and the B-vitamins and make similar claims to Emergen-C regarding immunity support and energy. There are 6 studies (21-26) on Berocca and Supradyn that are particularly pertinent to our proposed research investigating

Property of Haleon- Confidential

May not be used, divulged, published or otherwise disclosed without the consent of Haleon

CCI [REDACTED] Abbreviated Clinical Protocol Template v1.0

various parameters of perceived physical and mental energy as well as mood and stress. These studies have run from 28 days, 33 days, 4 weeks, 9 weeks, and 90 days. Physical and mental energy measured by validated tools such as the General Health Questionnaire-12 (GHQ-12) appear to be positively impacted more quickly than parameters like stress and emotional wellbeing as measured by scales such as the Profile of Mood States (POMS) as outlined in the table below.

Competitor supplement brands and their impact on physical and emotional measures of health.

Study	Brand	Duration	Results

1. Vitamins and psychological functioning: a mobile phone assessment of the effects of a B vitamin complex, vitamin C and minerals on cognitive performance and subjective mood and energy.
 
Human Psychopharmacology, Haskell et al. 2010.
	Berocca	28 days	
Participants in the vitamin/mineral group rated themselves as having greater 'physical stamina' across assessments and weeks. They also rated themselves as having had greater 'concentration' and 'mental stamina' during the working day. Participants in this group also reported greater subjective 'alertness' on Bond-Lader mood scales during the post-work assessment on day 14 and both the pre- and post-work assessments on day 28.

2. Effects of high-dose B vitamin complex with vitamin C and minerals on subjective mood and performance in healthy males.
 
Psychopharmacology, Kennedy et al. 2010.
	Berocca	33 days	
Vitamin/mineral supplementation led to significant improvements in ratings on the Perceived stress scale (PSS), General Health Questionnaire (GHQ-12) and the 'vigor' subscale of the Profile of Mood States (POMS). The vitamin/mineral group also performed better on the Serial 3s subtractions task and rated themselves as less 'mentally tired' both pre- and post-completion of the cognitive demand battery.

3. Acute and chronic effects of multivitamin/mineral supplementation on objective and subjective energy measures
 
Nutrition and Metabolism, Dodd et al. 2024.
	Berocca	28 days	
These findings extend on existing knowledge, demonstrating increased carbohydrate oxidation and increased energy expenditure in males following supplementation for the first time. Importantly, they show modulation of energy expenditure and subjective tiredness following a single dose, providing further evidence for acute effects of supplementation. Differential effects in men and women suggest that sex may play an important role in the effects of supplementation on energy metabolism.

4. Effects of Four-Week Supplementation with a Multi-Vitamin/Mineral Preparation on Mood and Blood Biomarkers in Young Adults: A
	Berocca Performance	4 weeks	
Compared to placebo, supplementation was associated with significantly lowered homocysteine and increased blood B-vitamin levels ($p < 0.01$). Supplementation treatment was also associated with

Property of Haleon- Confidential

May not be used, divulged, published or otherwise disclosed without the consent of Haleon

CCI [REDACTED] Abbreviated Clinical Protocol Template v1.0

Randomized, Double-Blind, Placebo-Controlled Trial. Nutrients, White et al, 2015.			significantly improved mood, as measured by reduced scores on the “depression-dejection” subscale of the Profile of Mood States ($p = 0.018$). These findings suggest that the four weeks of supplementation may have beneficial effects on mood, underpinned by elevated B-vitamins and lowered homocysteine in healthy young adults.
5.Effects of a multi-vitamin/mineral supplement on cognitive function and fatigue during extended multi-tasking Brain Performance and Nutrition Research, Haskell et al, 2015.	Supradyn	9 weeks	Those in the supplement group exhibited an attenuation of the negative effects of extended task completion on mood/fatigue. Multi-tasking performance for this group was also improved in terms of accuracy across all tasks, and on two of the individual tasks (Mathematical Processing and Stroop) in terms of both faster and more accurate responses.
6. The effect of 90-day administration of a high dose vitamin B-complex on work stress. Human Psychopharmacology Stough et al. 2011.	Supradyn	90 days	After individual differences in personality and work demands were statistically controlled, the vitamin B complex treatment groups reported significantly lower personal strain and a reduction in confusion and depressed/dejected mood after 12 weeks.

Consumer insights research points to the fact that consumers are interested in learning more about the scientific rationale behind the brand and want to understand the benefits of taking Emergen-C on a routine or daily basis. A study was developed to examine the effects of consistent daily Emergen-C use for 12 weeks during a fall/winter season. This timeframe was selected given the greater demand on the immune system during this time with higher incidence of cough, cold, and flu. The aim of this research is to determine how Emergen-C use can improve QoL in a real-world setting, that can be communicated to help consumers and healthcare professionals better understand the science behind the brand.

The aim of this randomized double-blind placebo-controlled clinical trial is to evaluate the effectiveness of daily consumption (over 12 weeks) of Emergen-C core super orange powder Emergen-C core powders on QoL in a real-world setting. This study will enroll a healthy adult population (aged 18-64 yrs.) in the United States into one of two study arms (study product, or placebo). It is hypothesized the study group will demonstrate a significant decrease in MFI (Multidimensional Fatigue Inventory) domain scores (i.e. meaning an improvement of energy level) from baseline compared to the placebo group following 12 weeks of daily supplementation.

Property of Haleon- Confidential

May not be used, divulged, published or otherwise disclosed without the consent of Haleon

CCI [REDACTED] Abbreviated Clinical Protocol Template v1.0

2 STUDY OBJECTIVES AND ENDPOINTS

Table 2-1 Study Objectives and Endpoints

Objectives	Endpoints
Primary	
To evaluate the effect of daily supplementation with Emergen-C in improving QoL parameters as measured by the Multidimensional Fatigue Inventory (MFI) domains, compared to placebo at Week 12.	Change from Baseline at Week 12 in: 
 • General Fatigue Domain score (items 1,5,12,16) • Physical Fatigue Domain score (items 2,8,14,20) • Reduced Activity Domain score (items 3,6,10,17) • Reduced Motivation Domain score (items 4,9,15,18) • Mental Fatigue Domain score (items 7,11,13,19)
Secondary	
To evaluate the effect of daily supplementation with Emergen-C in improving QoL parameters as measured by the Multidimensional Fatigue Inventory (MFI) domains, compared to placebo at Week 4 and 8.	Change from Baseline at Week 4 and 8 in: 
 • General Fatigue Domain score (items 1,5,12,16) • Physical Fatigue Domain score (items 2,8,14,20) • Reduced Activity Domain score (items 3,6,10,17) • Reduced Motivation Domain score (items 4,9,15,18) • Mental Fatigue Domain score (items 7,11,13,19)
To evaluate the effect of daily supplementation with Emergen-C in improving QoL parameters as measured by the Multidimensional Fatigue Inventory (MFI) individual items, compared to placebo at Week 4, Week 8 and Week 12.	Change from Baseline at Week 4, Week 8 and Week 12 for each of the individual items in the MFI.
To evaluate the effect of daily supplementation with Emergen-C in improving additional QoL parameters as measured by additional QoL Questions, compared to placebo at Week 4, Week 8 and Week 12.	Change from Baseline at Week 4, Week 8 and Week 12 for: 
 • Family support • Resilience • Ability to relax and unwind
Exploratory	
To evaluate the effect of daily supplementation with Emergen-C in improving additional QoL parameters as measured by additional QoL Questions, compared to placebo at Week 4, Week 8 and Week 12.	Number of days reported at Week 4, Week 8 and Week 12, for: 
 • days feeling unwell • days canceling plans • days with cough and cold symptoms • days sick in bed

Property of Haleon- Confidential

May not be used, divulged, published or otherwise disclosed without the consent of Haleon

Subgroup analyses for primary and secondary endpoints.	Subgroup analyses for 
 sex (male and female) age (18-34 and 35-64 years)
Safety	
To monitor the safety of the study treatment with daily use for 12 weeks.	The number of Treatment-emergent adverse events (TEAEs)

This study will be considered successful if daily use of Emergen-C supplementation improves QoL (as measured by any of the individual domain scores), compared to placebo at Week 12.

3 STUDY DESIGN

This is a randomized, double-blinded, placebo-controlled clinical trial in healthy male and female subjects, aged 18-64 years, evaluating the over-time effects of 12-weeks Emergen-C supplementation on QoL parameters in a real-world setting. A sufficient number of adults (approximately 430), aged 18-64 years, will be screened for eligibility. The study expects to enroll about 300 eligible subjects across the United States. Subjects will be enrolled into one of two study groups (at a 1:1 ratio) and will take one sachet of study product (Emergen-C or placebo) once daily in the morning at approximately the same time each day for 12 weeks. A total of approximately 240 subjects are expected to complete the study, approximately 120 in each study group.

Subjects will be recruited through targeted advertising on social media platforms. This study is entirely decentralized, and subjects will not be required to physically attend any on-site visits (only virtual visits). All study data will be collected remotely through a study platform using the subject's personal mobile device, tablet or computer.

Detailed study procedures can be found in Section 5 of the protocol.

4 STUDY POPULATION

4.1 Type and Planned Number of Subjects

This study will be conducted in healthy male and female subjects, aged 18-64 years (inclusive), and of any race/ethnicity. No discrimination of any kind (e.g. social class, gender, skin color, ethnicity) should preclude eligible participants from participating in the study. The study will aim to recruit a diverse population representative of the US census.

Sufficient subjects will be screened in order to enroll about 300 eligible subjects (approximately 150 subjects per study group) and approximately 240 subjects are expected to complete the study (approximately 120 subjects per study group, allowing for up to 20% dropouts). Potential participants will be recruited through targeted digital advertising campaigns.

Property of Haleon- Confidential

May not be used, divulged, published or otherwise disclosed without the consent of Haleon

CCI [REDACTED] Abbreviated Clinical Protocol Template v1.0

The study will be sufficiently powered to demonstrate statistically significant differences between Emergen-C core super orange powder compared to Placebo for QoL parameters as measured by the MFI at Week 12 (primary objective). A sample size of 120 evaluable subjects per treatment group will provide over 90% power to detect a mean difference of 0.5 standard deviations (27) Cohen's *d*), using a 2-tailed 2-sample t-test with a 1% significance level (Bonferroni-adjusted *p*-value). This effect is in line with the estimated minimal clinically important difference for the MFI in patients with lupus erythematosus (28).

The sample size calculation was performed using R software version 4.4.1.

This study can fulfill its objectives only if appropriate subjects are enrolled. All relevant medical and non-medical conditions should be taken into consideration when deciding whether a subject is suitable for this protocol. Subject eligibility to participate in the clinical study should be reviewed and documented by a delegated member of the investigator's study team before subjects are included in the study. The following eligibility criteria are designed to select subjects for whom participation in the study is considered appropriate.

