8 STATISTICAL CONSIDERATIONS AND DATA ANALYSES

8.1 Sample Size Determination

The primary objective for this study is to evaluate the over-time effects of Emergen-C Core Super Orange Powder on QoL parameters, as measured by the MFI domain scores (*General Fatigue, Physical Fatigue, Reduced Activity, Reduced Motivation, Mental Fatigue*), compared to placebo, when taken daily over 12 weeks.

A total of 300 subjects will be randomized (approximately 150 per group) to ensure sufficient power for the primary analysis. Assuming a maximum drop-out rate of 20%, approximately 240 evaluable subjects in total (120 per group) complete the entire study.

The sample size calculation was performed using R software version 4.4.1.

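### The test named in Protocol 4.1 gives 89.8% power at 120 per arm, just under the stated bound of more than 90%; a small wording error, not evidence of an underpowered trial

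*Protocol*

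**What the plan says.** The power statement is in Protocol 4.1 (Type and Planned Number of Subjects): "A sample size of 120 evaluable subjects per treatment group will provide over 90% power to detect a mean difference of 0.5 standard deviations". The same sentence gives the effect as Cohen's d and names the test: "using a 2-tailed 2-sample t-test with a 1% significance level". It describes the 1% level as Bonferroni-adjusted, which is 5% divided by the five MFI domains. Protocol 3 sets 1:1 allocation. The software is given as R 4.4.1, but no function or formula is named.

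Protocol 8.1 (Sample Size Determination) gives the numbers of subjects and no power, effect size or significance level: "A total of 300 subjects will be randomized (approximately 150 per group) to ensure sufficient power for the primary analysis". It then says: "Assuming a maximum drop-out rate of 20%, approximately 240 evaluable subjects in total (120 per group) complete the entire study". SAP 2.4, headed as the sample size calculation, also gives only numbers of subjects. The sentence in Protocol 4.1 is therefore the only power figure in either document.

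The planned analysis is not the t-test. Protocol 8.3.1 and SAP 5.4.1.2 specify a mixed model for repeated measures (MMRM) for each domain, with the baseline domain score as a covariate and Bonferroni-Holm across the five domains at Week 12.

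**The concern.** The statement is a bound, not a rounded figure. Power described as about 90% would cover 89.8%; power described as more than 90% does not. Size, effect, test, sidedness and level are all fixed in the text, so the bound either holds for that calculation or it does not.

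At stake is whether the stated justification for 120 evaluable subjects per arm is accurate. Someone who repeats the calculation with a standard t-test power routine will get a figure on the wrong side of the bound, and neither document gives another power statement to turn to. Nor is there any margin at the planning limit, because 150 per arm less 20% is exactly 120.

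**Working it through.** **Inputs**

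- Evaluable subjects per arm: n = 120 (Protocol 4.1)
- Standardised difference: d = 0.5 (Protocol 4.1)
- Test: two-sample t-test, two-sided, alpha = 0.01 (Protocol 4.1)
- Allocation: 1:1 (Protocol 3)
- Dropout: at most 20% (Protocol 4.1 and 8.1)

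**Step 1. Reproduce the plan's figure.** The normal approximation gives power = Φ(d·√(n/2) − z₀.₉₉₅).

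- d·√(n/2) = 0.5 × √60 = 3.873
- z₀.₉₉₅ = 2.576
- Power = Φ(3.873 − 2.576) = Φ(1.297) = 90.27%

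Solving the same formula for n at 90% power gives n = 2(z₀.₉₉₅ + z₀.₉₀)²/d² = 2 × (2.576 + 1.282)²/0.25 = 119.04, rounded up to 120 per arm. Dropout inflation gives 120/0.80 = 150 per arm, or 300 in total. So the plan's 120, 150 and 300, and its bound, all follow from the normal approximation. The documents do not say whether it was used.

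**Step 2. Compute power for the test that is named.** For a t-test with estimated variance, the statistic under the alternative is noncentral t.

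- Degrees of freedom: 2 × 120 − 2 = 238
- Noncentrality: 3.873, as above
- Two-sided 1% critical value: t₀.₉₉₅,₂₃₈ = 2.597
- Power = P(|T| > 2.597) = 89.80%

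A standard two-sample t-test power routine returns the same value.

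**Step 3. Size of the gap.**

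| Evaluable per arm | Exact t-test | Normal approximation |
|---|---|---|
| 119 | 89.50% | 89.99% |
| 120 | 89.80% | 90.27% |
| 121 | 90.08% | 90.55% |
| 150 | 95.82% | 96.03% |

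The t-test needs 120.7 per arm for 90% power, so 121 in practice. At 120 per arm, the difference detectable with 90% power is 0.5015 SD instead of 0.5 SD.

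**Step 4. Bearing on the trial itself.**

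- *Dropout.* Losing 30 of 150 per arm (20%) leaves 120. Losing 29 of 150 (19.3%) leaves 121, and the t-test then passes 90%.
- *Baseline adjustment.* If 0.5 SD refers to the unadjusted outcome, a baseline covariate with correlation ρ raises the effective d to 0.5/√(1 − ρ²). The documents give no ρ. Assuming ρ = 0.3, d becomes 0.524 and power 92.7%; assuming ρ = 0.5, d becomes 0.577 and power 96.9%.
- *Multiplicity.* Holm tests the smallest p-value at 1% and the others at less strict levels, so for any domain its power is never below that of Bonferroni at 1%.

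**The case against.** The strongest reply is that this is a choice of formula and not a mistake. The normal approximation is in common use, gives 90.3%, and returns exactly the protocol's 120 and 150 per arm. The exact figure differs by one subject per arm in a plan that describes its enrolment and completer numbers as approximate, and 120 is the count at the maximum assumed dropout. The t-test is also only a planning device. The MMRM uses the baseline score, Holm is at least as powerful as Bonferroni, and subjects who drop out after a Week 4 or Week 8 assessment stay in the modified intention-to-treat analysis. In addition, Protocol 2 counts the study a success if any one domain improves. If all five domains shifted by 0.5 SD, the chance that at least one passes the 1% level is about 95% to 99% by simulation, for assumed correlations between domains of 0.9 down to 0.5 (not given in the documents).

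Most of this stands, and it limits how far the point goes. A reader might infer from 89.8% that the trial will fall short of its intended power. The documents do not support that: the figure applies to a simpler test than the one planned, at the least favourable retention the plan allows.

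The reply does not rescue the sentence. Protocol 4.1 names a t-test, and the normal approximation treats the variance as known. The power sentence attaches no qualifier to 120, and it claims a bound. The gains from the MMRM depend on a baseline correlation that is not given and on 0.5 SD being on the unadjusted scale, which the protocol does not specify. They may make the trial's real power higher, but they are not the calculation reported.

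**Conclusion.** The point holds as a minor error of statement. For the calculation that Protocol 4.1 describes, power is 89.8%, not more than 90%. The excess is 0.2 percentage points, equivalent to one evaluable subject per arm or 0.0015 SD in the detectable difference. This result uses only inputs printed in the protocol and the exact distribution of the named test.

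It does not follow that the trial is underpowered or that 300 randomized subjects are too few. The planned analysis will probably match or exceed the t-test's power, on the assumption that 0.5 SD is on the unadjusted scale. No decision on size, conduct or analysis changes. The statement in Protocol 8.1 that power is sufficient is not contradicted by 89.8%, so there is no second error there.

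**What to change.** In Protocol 4.1, replace the claim of more than 90% power with: approximately 90% power (89.8%, two-sided two-sample t-test, alpha = 0.01). If the sponsor prefers to keep the bound, the sentence would have to say that it comes from the normal approximation (90.3%).

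The cost is one sentence, and a stated figure that is slightly less favourable. The sample size need not change. Repeating the corrected sentence in Protocol 8.1 and SAP 2.4 would help a reader who looks for the calculation there, but it corrects no error and is optional.
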